4.8 Management of Adverse Events and Supportive Care Guidelines

Immuno-oncology agents are associated with AEs that can differ in severity and duration compared to AEs caused by other therapeutic classes. APX005M, cabiralizumab and nivolumab are considered immuno-oncology agents in this protocol. Early recognition and management of AEs associated with immuno-oncology agents may mitigate severe toxicity. Subjects should receive appropriate supportive care measures as deemed necessary by the treating Investigator. Suggested supportive care measures for the management of AEs with **potential immunologic etiology** are outlined below. These treatment guidelines are intended to be applied when the Investigator determines the events to be related to the APX005M + cabiralizumab \pm nivolumab combination and should not substitute for investigational product dose delays and/or modifications. Additional guidance for management of AEs with potential immunologic etiology is provided in the APX005M, cabiralizumab and nivolumab Investigator's Brochures.

If after evaluation the event is determined by the Investigator not to be related to investigational products, the Investigator does not need to follow the treatment guidance outlined in this section.

For each disorder, attempts should be made to rule out other causes such as metastatic disease, or bacterial/viral infection, which might require additional supportive care.

Steroid tapering may be necessary for prolonged exposures to corticosteroids, or if symptoms worsen when the corticosteroid dose is decreased.

Diarrhea/Colitis

Subjects should be carefully monitored for signs and symptoms of enterocolitis (such as diarrhea, abdominal pain, blood or mucus in stool, with or without fever) and of bowel perforation (such as peritoneal signs and ileus). All subjects who experience diarrhea/colitis should be advised to drink liberal quantities of clear fluids. If sufficient oral fluid intake is not feasible, fluid and electrolytes should be substituted via IV infusion. For Grade 2 or higher diarrhea, consider GI consultation and endoscopy to confirm or rule out colitis.

- **Grade 1-2:** for subjects developing Grade 1–2 diarrhea loperamide (2 mg every 2 hours) is strongly recommended at the first onset of symptoms. For subjects with persistent diarrhea despite the use of loperamide ($>$ 7 days or recurrent) or Grade 2 colitis, the use of oral corticosteroids (0.5–1 mg/kg/day methylprednisolone or oral equivalent) is recommended. Other antidiarrheal agents (e.g. octreotide) may be used if necessary. When symptoms improve to Grade 1, steroids may be tapered as deemed appropriate by the investigator. If steroids are administered for over weeks, consider prophylactic antibiotics for opportunistic infections. If symptoms worsen or persist $>$ 5 days despite steroids treatment, treat as grade 3–4.
- **Grade 3-4:** treat with corticosteroids (1–2 mg/kg/day methylprednisolone or IV equivalent) followed by oral corticosteroids until symptoms improve to Grade 1 or less. Add prophylactic antibiotics for opportunistic infections and consider lower endoscopy.

If persist or recurs continuously after improvement, consider infliximab 5mg/kg (unless sepsis or perforation is detected).

Creatinine Elevation

- **Grade 2-3:** treat with corticosteroids (0.5–1 mg/kg/day methylprednisolone or oral equivalent) until symptoms improve to Grade 1 or less. Consider renal biopsy with nephrology consult. If persist > 14 days treat as grade 4.
- **Grade 4:** treat with corticosteroids (1–2 mg/kg/day methylprednisolone or IV equivalent) followed by oral corticosteroids until symptoms improve to Grade 1 or less. Consider renal biopsy and consult nephrologist. Add prophylactic antibiotics for opportunistic infections. If worsen consider clinical referrals as needed.

Pneumonitis

- **Grade 2:** Treat with IV or oral corticosteroids until symptoms improve to Grade 1 or less. Consider prophylactic antibiotics for opportunistic infection. Consider bronchoscopy, lung biopsy and hospitalization. If does not improve after 2 weeks treat as grade 3-4.
- **Grade 3-4:** Consider pulmonary or infectious disease consults. Hospitalize and treat immediately with IV corticosteroids (2–4 mg/kg/day methylprednisolone or IV equivalent). Add prophylactic antibiotics for opportunistic infections. Consider bronchoscopy and lung biopsy. If does not improve after 48h or worsens, add additional anti-inflammatory measures (e.g. cyclosporine, IVIG, mycophenolate mofetil)

Liver Function Tests

- **Grade 3 transaminitis:** Monitor liver function tests more frequently until returned to Grade 2 or less. Start oral or IV corticosteroids if transaminitis > 5 to ≤ 12 x ULN persists for > 7 days. Continue steroids until returns to Grade 1 or less. If the first transaminase value is 12X ULN or greater, start steroids immediately.
- **Grade 4 ALT and/or AST elevations, or grade 4 bilirubin increase:** Treat with IV corticosteroids for 24-48 hours followed by oral corticosteroids until improvement to Grade 1 or less. If worsening in 3-5 days, administer additional immunosuppressive measures (e.g. mycophenolate mofetil), as needed. Consider adding prophylactic antibiotics for opportunistic infections. Consult gastroenterologist.
- **Grade ≥ 2 transaminitis (> 3 x ULN) and total bilirubin > 2 x ULN:** Treat with IV corticosteroids (1–2 mg/kg/day methylprednisolone or IV equivalent) followed by oral corticosteroids. Consider adding prophylactic antibiotics for opportunistic infections. Consult gastroenterologist. Continue steroids until symptoms improve to Grade 1 or less. If worsening in 3-5 days, add mycophenolate mofetil 1g BID. If no improvement consider additional immunosuppressive measures per local guidelines.

Endocrinopathy

- **Asymptomatic TSH elevation:** monitor fT4 if TSH is $< 0.5 \times$ LLN, $> 2 \times$ ULN or consistently out of range in two subsequent measurements.

Symptomatic endocrinopathy: evaluate endocrine function. For abnormal laboratory results initiate hormone repletion.

- **Suspicion of adrenal crisis:** rule out sepsis, administer IV fluids, treat as for symptomatic endocrinopathy. Otherwise, administer stress dose of IV steroids with mineralocorticoid activity.

Skin Adverse Events.

- **Grade 1-2:** symptomatic treatment (e.g. antihistamines, topical steroids). If unresponsive, consider steroid burst. If worsens treat as grade 3-4.
- **Grade 3-4:** Consider skin biopsy. Treat with steroids as deemed appropriate by the treating physician (1–2 mg/kg/day methylprednisolone or IV equivalent).

Infusion Reaction/Cytokine Release Syndrome

Precautions should be observed during the administration of APX005M, nivolumab and cabirizumab. Emergency agents including oxygen, oral and endotracheal airways, intubation equipment epinephrine, antihistamines, and corticosteroids should be available and used if required at the Investigator's discretion.

Subjects should be instructed that symptoms associated with cytokine release syndrome/infusion reaction can occur within 48 hours following the administration of the investigational products, and if such symptoms develop while they are at home, they should contact the Investigator and/or seek emergency medical care if appropriate.

- **Grade 1:** decrease infusion rate as per protocol
- **Grade 2:** Stop infusion and treat symptoms following guidelines in Table 4. If symptoms resolve within two hours, the infusion may be restarted at 50% of the original infusion rate (e.g., from 100 mL/hr to 50 mL/hr).
- **Grade 3-4:** stop infusion and treat symptoms following guidance in Table 4. If subjects resume study treatment after previously having a grade 3 infusion-related reaction and/or cytokine release syndrome, a 48-hour inpatient observation period is mandatory after the infusion to perform frequent vital sign checks. If grade ≥ 3 infusion-related reaction/cytokine release syndrome does not recur upon rechallenge, further cycles may be administered in the outpatient setting.

Table 4: Guidelines for Management of Cytokine Release/Infusion Reaction Symptoms

Suspected Cytokine Release/Infusion-related Toxicity	Recommended Treatment

 • Mild toxicity requiring symptomatic treatment only (e.g., fever, nausea, fatigue, headache, myalgia, malaise) 	
 • Vigilant supportive care • Maintain adequate hydration • Antipyretics, non-steroidal anti-inflammatory drugs, antihistamines, anti-emetics, analgesics as needed • In case of mild symptoms persisting for > 24 hours assess for infections; empiric treatment

	of concurrent bacterial infections

 • Symptoms or clinical findings requiring and responding to moderate intervention, such as: 
 ○ O₂ requirement < 40% ○ Hypotension responsive to fluids ± low dose of one vasopressor (e.g., < 50 mg/min phenylephrine) ○ CTCAE v5.0 Grade 2 organ toxicity 	
 • All of the above • Monitor cardiac and other organ functions closely • Corticosteroids if not resolving with measures above

 • Symptoms or clinical findings requiring aggressive intervention, such as: 
 ○ O₂ requirement ≥ 40% ○ Hypotension requiring high dose or multiple vasopressors ○ Ventilator support required • CTCAE v5.0 Grade ≥3 organ toxicity 	
 • All of the above • Monitor cardiac and other organ functions closely • Corticosteroids if not resolving with measures above • Tocilizumab if not responsive to steroids and other measures

Neurological Toxicity

- **Grade 2:** symptomatic treatment per local guidelines. Consider steroids (0.5–1 mg/kg/day methylprednisolone or PO equivalent). If worsen treat as grade 3-4.
- **Grade 3-4 or grade 2 for >28 days:** obtain neurological consult and treat symptoms per local guidelines. Administer corticosteroids (1–2 mg/kg/day methylprednisolone or IV equivalent). Add prophylactic antibiotics for opportunistic infections. Continue steroids until symptoms improve to Grade 2 or less. If symptoms worsen or for atypical presentation consider IVIG, high doses steroids (e.g. 1g methylprednisolone) or other immunosuppressive measures per local guidelines.

Periorbital Edema:

- **Grade 1:** Monitor edema
- **Grade 2-4:** Consider IV or oral corticosteroids until symptoms improve to Grade 1 or less. Consider adding eye drops, or analgesics as needed. Seek ophthalmologic consult if needed.

Uveitis:

- **Grade 1:** Watch for worsening of symptoms including visual disturbances, light sensitivity, decrease vision, monitor weekly.
- **Grade 2-4:** Treat with IV or oral corticosteroids until symptoms improve to Grade 1 or less. Consider additional immunosuppressive agents if not responsive (such as infliximab). Consider adding prophylactic antibiotics for opportunistic infections and seek ophthalmologic consult.

CK Increase:

- **CK > 10x ULN:** Consider measuring CK isoenzymes as clinically indicated. If CK isoenzymes are abnormal consider measuring troponin levels and other assessments (including uromyoglobin) as clinically indicated. If CK isoenzymes are normal monitor CK level as clinically indicated.
- **CK > 15x ULN:** If clinically indicated, measure CK isoenzymes and test more frequently until returned to Grade 2. If CK isoenzyme panel is normal continue monitoring the subject. If CK isoenzyme panel is abnormal then consider measuring troponins.

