3.1.2.1.1 Dose Limiting Toxicity

A DLT is defined as any of the following AE (graded using National Cancer Institute [NCI] Common Terminology Criteria for Adverse Events [CTCAE] v5.0), which occurs during the first 28-days of cabiralizumab/APX005M or nivolumab/cabiralizumab/APX005M administration that is not clearly due to a cause other than the study medication (e.g., disease under study, car accident).

1. Grade 4 neutropenia or grade 4 thrombocytopenia lasting ≥ 7 days
2. Neutropenic fever of any duration
3. Grade ≥ 3 thrombocytopenia if associated with:
 - a. Clinically significant bleeding or requirement for platelet transfusion, or
 - b. A life-threatening bleeding event which results in urgent intervention and admission to an Intensive Care Unit
4. Any grade ≥ 3 non-hematologic toxicity (not laboratory) **with the exception of:**
 - Grade 3 tumor flare (defined as local pain, irritation, or rash localized at sites of known or suspected tumor)
 - Grade 3 joint pain
 - Grade 3 fatigue lasting less than 1 week
 - Serum elevations of CK $> 15X$ ULN and $\leq 20X$ ULN that last for < 7 days
 - Grade 3 or Grade 4 electrolyte abnormalities that are not complicated by associated clinical adverse experiences, last less than 72 hours and either resolve spontaneously or respond to conventional medical intervention
 - Grade 3 nausea, vomiting, or diarrhea lasting less than 72 hours, and either resolves spontaneously or responds to conventional medical intervention including adequate anti-emetics or other supportive care
 - Grade 3 or grade 4 elevation of amylase or lipase not associated with clinical or radiographic evidence of pancreatitis
 - Grade 3 fever not associated with hemodynamic compromise (eg, hypotension, clinical or laboratory evidence of impaired end-organ perfusion)
 - Grade 3 endocrinopathy that is well controlled by hormone replacement
 - Grade 3 infusion reaction that returns to Grade 1 in < 6 hours
5. Any Grade ≥ 3 non-hematologic laboratory value if:
 - a. Immune suppression other than corticosteroids is required to treat the subject, or
 - b. The abnormality itself solely leads to hospitalization, or
 - c. The abnormality persists for > 1 week. For AST/ALT $> 12X$ ULN, DLT is defined as not improving after > 7 days or the value increases by more than $5X$ ULN over 72 hours;

e.g. if an AST of 300 rises to 500 in 72 hours, where AST 36 is ULN, a rise of 200 is greater than 5X ULN (180) and would be considered a DLT

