3.1.5 Study Duration

Patients who receive study drug(s) may continue as long as they experience clinical benefit in the opinion of the Investigator or until unacceptable toxicity or symptomatic deterioration attributed to disease progression as determined by the Investigator after an integrated assessment of radiographic data, biopsy results (if available), and clinical status, or withdrawal of consent. The maximum time allowed time on study treatment will be up to 2 years unless the study is terminated sooner by the Sponsor.

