4.9 Criteria for Holding, Discontinuing, or Modifying Study Drug

Management of suspected adverse drug reactions may require temporary treatment hold (until re-treatment criteria are met), reducing the dose of APX005M, or discontinuation of some or all investigational products as per Table 5. If a subject experiences several toxicities, the recommended dose modification should be based on the highest grade toxicity.

Up to two dose reductions are permitted for APX005M. There are no dose reductions for cabiralizumab or nivolumab.

Table 5: Criteria for Holding, Discontinuing, or Modifying Study Drug

	Toxicity	Grade	APX005M	Cabiralizumab	Nivolumab
Gastrointestinal AEs	Diarrhea/colitis	2-3	1 st occurrence: Hold	Hold	Hold
			2 nd occurrence: dose reduction [¥]	If not improving in 28 days with oral steroids: Discontinue	If not improving in 28 days with oral steroids: Discontinue
	Vomiting	4	Discontinue	Discontinue	Discontinue
Endocrine AEs	Hypophysitis/ Endocrinopathies	2-4	Hold only if clinically unstable	Hold only if clinically unstable	Hold only if clinically unstable

	Toxicity	Grade	APX005M	Cabirizumab	Nivolumab
	Hyperthyroidism	2-4	Hold only if clinically unstable	Hold only if clinically unstable	Hold only if clinically unstable
Hepatic AEs	Increased AST/ALT	3 (> 5 to ≤ 12x ULN) and bilirubin <2x ULN	Continue	Continue	Continue
		3 (> 12x ULN) for >14 days and not decreasing on steroids and bilirubin <2x ULN	Hold	Hold	Hold
		2-3 and total bilirubin >2x ULN or 3x baseline for patients with Gilbert's syndrome and no cholestasis or INR >1.5 not on warfarin	Discontinue	Discontinue	Discontinue
		4	Discontinue	Discontinue	Discontinue
Increased bilirubin	Increased bilirubin	2	Hold	Hold	Hold
		3	Hold If >48 hours with no cholestasis or > 5 days with cholestasis: Discontinue	If >48 hours with no cholestasis or > 5 days with cholestasis: Discontinue	If >48 hours with no cholestasis or > 5 days with cholestasis: Discontinue
		4	Discontinue	Discontinue	Discontinue

	Toxicity	Grade	APX005M	Cabiralizumab	Nivolumab
Skin AEs	Rash or other skin toxicity	3	Hold If not improving in 28 days: Discontinue	Hold If not improving in 28 days: Discontinue	Hold If not improving in 28 days: Discontinue
		4	Hold If not improving in 28 days: Discontinue	Hold If not improving in 28 days: Discontinue	Discontinue
Neurological AEs	Neurological Toxicity	2	Continue	Continue	Hold
		3	Hold	Hold	1 st occurrence: Hold 2 nd occurrence: Discontinue
		4	Hold	Hold	Discontinue

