 - Serum PK at 168 hours (\pm 6 hours) from start of infusion (APX005M)
- AE reporting, if applicable
- Review of concomitant medications

5.2.1.10 Subsequent Cycles, Day 1

A \pm 2 day window is allowed for Day 1 in subsequent cycles post Cycle 2, Day 1.

Dosing will be discontinued if the patient experiences either disease progression or unacceptable toxicity.

At each infusion visit, patients are to remain at the study site after each administration of APX005M until completion of all post-dose assessments for safety monitoring. The following assessments will be performed at each visit unless otherwise noted (Appendix A).

Prior to study drug infusion (within \leq 72 hours unless otherwise stated):

- Physical examination including weight
- Vital signs (blood pressure, pulse, respiratory rate and temperature in resting position after 5 minutes rest)
- ECOG performance status evaluation
- Clinical safety labs (as described in Appendix A; results must be reviewed before dosing)
- Urine pregnancy test (β -hCG) for women of childbearing potential within 24 hours of dosing
- Blood collection for:
 - Biomarker blood sample collection (analyses described in Appendix D)
 - Serum PK (for APX005M only) on Day 1 of every 3rd cycle (Cycles 3, 6, 9, 12, etc.) during dose escalation
 - pre-infusion (APX005M)
 - end of infusion (APX005M)
 - Pre-treatment serum anti-drug antibody (ADA) levels (for APX005M only) on Day 1 of every 3rd cycle (Cycles 3, 6, 9, 12, etc.) during dose escalation
- Body and brain imaging will be performed every 8 weeks (\pm 7 days) from the first dose for the first 4 months for patients who remain on treatment and every 12 weeks (\pm 7 days) thereafter and 28 days (\pm 7 days) after the last dose of study treatment. See Appendix A for further details.
- Biopsy at primary tumor or metastatic site will be collected within 7 days prior to Cycle 5 Day 1 and at least 24 hours prior to dosing
- AE reporting, if applicable
- Review of concomitant medications

- Study drug administration

Pre- and post-study each drug administration: Vital signs: Patients can be discharged from clinic if: oxygen saturation > 90%, SBP no more than 30 mmHg below baseline, heart rate no more than 30 beats per minute above baseline, unless febrile. If febrile, subjects can be discharged home as long as their temperature is less than 101 degrees Fahrenheit.

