7.4 Safety Analyses

Safety analyses will be performed for all treated patients. Incidence of AEs, clinical laboratory information, vital signs, ECOG performance status, weight, and ECGs will be tabulated and summarized.

Incidence of AEs will be summarized overall and with separate summaries for SAEs, AEs leading to discontinuation, AEs leading to death, and NCI-CTCAE v5.0 Grade 3 or higher AEs.

Weight and vital signs will be summarized descriptively (n, mean, standard deviation, median, minimum, and maximum). ECOG performance status will be summarized categorically and descriptively.

Shift tables displaying patient counts and percentages classified by baseline grade and maximum grade on treatment will be provided for laboratory data by cohort and overall. A marked laboratory change is defined as a shift from a baseline Grade 0 to Grade 3 (non-hematologic) or Grade 4 (hematologic) on treatment, or a shift from a baseline Grade 1 to Grade 4 on treatment. The number and percentage of patients with marked laboratory changes will be tabulated by cohort and overall.

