Long-Term Follow-up Contact ^t											x

Notes for Phase 1 Dose Escalation Schedule of Assessments

- a. Unless specified, prior to infusion procedures are to be completed within 24 hours of scheduled time point and to be synchronized with administration of assigned study drug. Any clinical assessment, laboratory study, or additional non-specified tests may be obtained at any time, if clinically indicated.
- b. Each cycle will be 14 days long, with administration of cabiralizumab, APX005M, ± nivolumab on Day 1; a \pm 2 day window is allowed for Day 1 starting with Cycle 3.
- c. Standard physical examination will be performed as determined by the Investigator, particularly to follow physical findings to resolution. Targeted physical exams should be conducted at any time to follow up on AE reports. A symptom-directed physical exam can be performed for days 2, 3, and 8 of Cycles 1 and 2.
- d. Height is only required to be recorded at screening. Weight is required to be recorded at Day 1 of each cycle. Dose will be adjusted only if weight change is $>10\%$ from first dose on Cycle 1 Day 1.
- e. Vital signs include pulse, respiratory rate, blood pressure, and temperature in the resting position (sitting or supine). Measure prior to dose and after completion of each IV infusion for all cycles. For Day 1 of Cycles 1 and 2 only, additionally measure vital signs 4 hours (± 30 min) post-APX005M infusion. Pulse oximetry is performed at rest prior to dosing for day 1 of each cycle and otherwise as clinically indicated. At the Investigator's discretion, vital sign monitoring may be extended beyond the time points specified. Additional measures should be performed as clinically indicated.
- f. Patient ECOG Status assessments are to be performed within 72 hours prior to dosing (Day 1 of each cycle).
- g. Screening labs include serology for Hepatitis B (HBsAg) and Hepatitis C (HCV antibody).
- h. Clinical Safety Labs:

Hematology including CBC with differential, platelets, hemoglobin, hematocrit, RBC, and RBC indices

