Chemistry includes CK (creatinine kinase), AST (aspartate transaminase), ALT (alanine transaminase), alkaline phosphatase, bicarbonate, bilirubin, (direct and total), BUN (blood urea nitrogen), calcium, chloride, creatinine, glucose, LDH (lactate dehydrogenase), phosphorus, potassium, sodium, and, if applicable, serum pregnancy. Albumin, amylase, lipase, thyroid panel includes TSH, Free T4, PT/INR, and PTT (aPTT) perform at Screening and as indicated. If CK elevation is clinically significant, obtain troponins (cardiac and skeletal), CK isoenzymes, aldolase, and ECG; repeat CK and these additional tests within 48 hours or other interval as clinically indicated, until resolved or stable. If either AST or ALT is elevated, obtain total serum bilirubin, alkaline phosphatase; repeat within 48 hours or other interval, as clinically indicated, until resolved or stable. Additional tests may be obtained at any time, if clinically indicated.

Urinalysis: Urine dipstick will only be done at screening, and when clinically indicated.

- i. Obtain ECG records at Screening and the Day 28 post last infusion End-of-Treatment Visit. Additional ECGs should be obtained at any time, if serum CK or cardiac troponin is elevated; if abnormal (excluding sinus tachycardia), ECGs should be obtained (if clinically indicated), until the abnormality is resolved or clinically stable. Additional ECGs may be obtained at any time, if clinically indicated. ECGs for each patient should be obtained from the same machine whenever possible. To minimize variability, it is important that patients be in a resting position for at least 5 minutes prior to each ECG evaluation. Body position should be consistently maintained for each ECG evaluation to prevent changes in heart rate. Environmental distractions (e.g., television, radio, conversation) should be avoided during the pre-ECG resting period and during ECG recording.

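### Section 4.8 acts on TSH in asymptomatic patients, but neither schedule of assessments fixes a TSH test after screening, so asymptomatic thyroid toxicity is found only where a clinician chooses to test

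*Combined protocol and SAP*

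**What the plan says.** The endocrinopathy guidance in Section 4.8 has a separate item for raised or lowered TSH without symptoms. Free T4 is to be monitored in three situations: TSH below 0.5 times the lower limit of normal, TSH above twice the upper limit, or TSH "consistently out of range in two subsequent measurements".

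The timing of TSH is set in note h of Appendix A (dose escalation) and, in the same words, note h of Appendix B (phase 1b): "thyroid panel includes TSH, Free T4, PT/INR, and PTT (aPTT) perform at Screening and as indicated". The visit lists in Section 5.2 refer to the appendices for clinical safety labs and name no thyroid test of their own. Section 5.3.1 names none either. Note a of each appendix leaves room for discretion: "additional non-specified tests may be obtained at any time, if clinically indicated".

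Section 7.4 summarises laboratory data in shift tables "classified by baseline grade and maximum grade on treatment", by cohort and overall. Section 3.1.5 sets the treatment limit: "The maximum time allowed time on study treatment will be up to 2 years".

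**The concern.** A rule for asymptomatic patients needs a result that symptoms did not prompt. CK, AST, ALT and bilirubin have such results, because note h lists them without restriction among the labs drawn at the marked visits. TSH does not.

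Two things follow. First, whether the Section 4.8 rule is ever triggered in a given patient depends on who happened to be tested. Second, thyroid abnormalities are detected unevenly, so a thyroid frequency cannot be read as an incidence or compared fairly between cohorts.

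This matters because safety and tolerability are primary objectives in both phases (Sections 2.1.1 and 2.2.1) and endocrine toxicity is expected. Section 1.3.6.2.2 describes nivolumab endocrinopathies treated with hormone replacement. Section 1.3.6.1.3.3 reports a Grade 3 hypopituitarism attributed to cabiralizumab and nivolumab. Table 5 has endocrine rows.

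**Working it through.** The plan states no figure to reproduce. The check compares the rule with the schedule and counts tests.

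**What the rule needs.** The two threshold conditions need at least 1 on-treatment TSH. The repeat condition needs at least 2 measurements.

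**What the schedule supplies**

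| Source | Fixed TSH on treatment |
|---|---|
| Appendix A, note h (dose escalation) | 0; screening only, then as indicated |
| Appendix B, note h (phase 1b) | 0; same wording |
| Section 5.2 visit lists | 0; they defer to the appendices |
| Section 5.3.1 | 0; no thyroid schedule |

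**Exposure over which this applies.** The maximum is 2 years, or 104 weeks. With 14-day cycles, 104 / 2 = 52 cycles. The count is therefore 1 fixed TSH (screening) and 0 on treatment across up to 52 cycles.

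**Does *as indicated* mean at the marked visits?** Screening is itself a marked visit for these labs, so on that reading the express mention of screening would be redundant. In the same note, urine dipstick is likewise limited to screening and clinical need. The natural reading is screening, then discretion.

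**What an existing sampling schedule would supply.** In dose escalation, PK and anti-drug antibody samples are drawn "on Day 1 of every 3rd cycle (Cycles 3, 6, 9, 12, etc.) during dose escalation" (Section 5.2.1.10). Section 5.2.2.6 uses the same cycles after Cycle 1 in phase 1b.

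- Number of draws: cycles 3, 6, ..., 51, so floor(52 / 3) = 17.
- With one at the 28-day End-of-Treatment visit: 17 + 1 = 18 at most.
- Nominal day of Day 1 of cycle c: 14(c − 1) + 1. Cycle 3 is Day 29, Cycle 6 Day 71, Cycle 9 Day 113 and Cycle 12 Day 155.
- Two values, enough for the repeat condition, exist by Day 71. Four exist within about six months, the period in which Section 1.3.6.2.2 says most nivolumab select adverse events occurred.

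**Effect on decisions.** For endocrinopathy and hyperthyroidism, Table 5 in Section 4.9 says "Hold only if clinically unstable". Section 4.7 allows retreatment with Grade 2 endocrinopathy. Section 3.1.2.1.1 exempts from dose-limiting toxicity "Grade 3 endocrinopathy that is well controlled by hormone replacement". Missed asymptomatic thyroid change would rarely alter dosing, escalation or response.

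**The case against.** The strongest reply is that note h is ambiguous. Where it plainly means discretion it adds the word *clinically*, which the thyroid sentence lacks, and note n of Appendix A uses *as indicated* to point to a schedule in Appendix C. The safety-lab row is marked at every Day 1. But note n names the place where its schedule stands and note h names none, and the redundancy argument still favours discretion. If sites do read it the other way, the wording needs correcting anyway.

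Second, Section 5.3.1 says chemistry abnormalities found at screening are followed with further laboratory data. That stands, and it gives a patient with an abnormal baseline TSH a route to repeat values. It does not reach a new change after a normal baseline, which is what treatment toxicity would look like in most patients.

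Third, Section 4.8 offers suggested measures, and two of its three conditions need only one value, which a clinician may order at any time. This is correct: the rule can operate ad hoc and there is no strict contradiction. It does not supply the data needed for systematic detection. The Investigator's Brochures may say more about thyroid monitoring, but they are not among the documents reviewed and cannot be relied on here.

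Finally, the consequences for dose and efficacy are slight, and no event rate is available. Both points limit the weight of the concern. They do not remove it, because safety is itself a primary objective.

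**Conclusion.** The concern holds. Followed as written, the plan gives no fixed on-treatment TSH in either phase, so new asymptomatic thyroid change after a normal baseline is found only where a clinician happens to test. Any on-treatment thyroid results in the Section 7.4 summaries would describe a selected subset.

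The conclusion rests on reading note h as screening plus discretion. Under-ascertainment is an inference from the lack of a testing prompt in patients without symptoms. Its size cannot be estimated, because the documents give no thyroid event rate. The 52-cycle figure is a maximum, and patients who stop earlier have less exposure to the gap. This should be corrected, but it does not threaten the escalation decisions or the response-rate analysis.

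**What to change.** In note h of Appendices A and B, move TSH into the scheduled on-treatment safety labs: Day 1 of every third cycle (3, 6, 9 and so on), with the existing PK and antibody draw, and the 28-day End-of-Treatment visit. Trigger free T4 by the Section 4.8 limits, and keep *as indicated* for extra tests. In Section 7.4, report thyroid results with the number of patients tested on treatment as the denominator.

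The cost is a wording change and one more assay at visits where blood is already drawn: at most 17 on treatment plus 1 at End of Treatment per patient, with free T4 when triggered. No visit is added. The first test, at nominal Day 29, falls after the 28-day dose-limiting toxicity interval, so this schedule does not inform escalation decisions. That is acceptable given how little thyroid laboratory change bears on them.
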